8.14. Blood for Exploratory Testing

At entry, DNA will be collected to evaluate polymorphisms related to IL28B and future evaluation of association with study outcomes including infection. Serum and plasma will also be collected as part of the JHU COVID-19 biorepository. If resources are available, a multiplex cytokine panel will be performed to evaluate for differences in longitudinal peripheral cytokine levels comparing infected individuals that received the study drug compared to those that received placebo. 6 mL of plasma in EDTA tubes and 6 mL of serum in SST tubes will be collected and stored, in addition to the serum collected for IL28B. 30 mL of blood will be collected at each timepoint.

8.15. Adverse Event Evaluation

An AE is any untoward medical occurrence in a clinical study participant administered a medicinal (investigational or non-investigational) product. An AE does not necessarily have a causal relationship with the intervention. An AE can therefore be any unfavorable and unintended sign (including an abnormal finding), symptom, or disease temporally associated with the use of a medicinal (investigational or non-investigational) product, whether or not related to that medicinal (investigational or non-investigational) product (Definition per ICH).

This includes any occurrence that is new in onset or aggravated in severity or frequency from the baseline condition, or abnormal results of diagnostic procedures, including laboratory test abnormalities.

All adverse events, both serious and nonserious, will be collected from the time of informed consent through protocol Day 28. Participants will be asked open-ended and non-leading questions to evaluate for adverse events. Participants will also be asked directed questions to evaluate the presence or absence of fever, chills, arthralgia, myalgia, or pain. To monitor for injection site reactions, participants will be asked directed questions regarding pain, erythema, induration, or pruritus. The injection site will be inspected via video check-in on Day 7.

Adverse events will be collected directly in REDCap though a link embedded in the eMocha app. Participants will include their eMocha app username and cell phone number on the survey. For participants who are unable to access or use eMocha, surveys will be interviewer-administered over the phone by trained research staff.

8.15.1 Investigator's Assessment of Adverse Events

The determination of seriousness, severity, and causality will be made by an on-site investigator who is qualified (licensed) to diagnose adverse event information, provide a medical evaluation of adverse events, and classify adverse events based upon medical judgment. This includes but is not limited to physicians, physician assistants, and nurse practitioners.

Adverse Events will be graded according to the Common Terminology Criteria for Adverse Events (CTCAE) v5.0.

8.15.2 Serious Adverse Events

An SAE based on ICH and European Union Guidelines on Pharmacovigilance for Medicinal Products for Human Use is any untoward medical occurrence that at any dose:

- Results in death
- Is life-threatening
(The participant was at risk of death at the time of the event. It does not refer to an event that hypothetically might have caused death if it were more severe.)
- Requires inpatient hospitalization or prolongation of existing hospitalization
- Results in persistent or significant disability/incapacity
- Is a congenital anomaly/birth defect
- Is a suspected transmission of any infectious agent via a medicinal product
- Is Medically Important*

*Medical and scientific judgment should be exercised in deciding

whether expedited reporting is also appropriate in other situations, such as important medical events that may not be immediately life threatening or result in death or hospitalization but may jeopardize the participant or may require intervention to prevent one of the other outcomes listed in the definition above. These should usually be considered serious.

An exception to expedited reporting is progression of the disease under investigation; worsening of respiratory function due to COVID-19 requiring hospitalization will be reported as an adverse event but will not be reported as a SAE.

Any SAEs will be reported to the JHMIRB within 24 hours of the study team becoming aware of the event.

Initial reporting to the FDA: The Investigator/ designee will report any suspected adverse reaction or adverse reaction to study treatment that is both serious and unexpected.

Unexpected serious suspected adverse reactions and observations from animal studies suggesting significant risk to human subjects must be reported to FDA as soon as possible but no later than within 15 calendar days following the Investigator's initial receipt of the information.

Unexpected fatal or life-threatening suspected adverse reactions represent especially important safety information and must be reported to FDA as soon as possible but no later than 7 calendar days following the Investigator's initial receipt of the information.

•Follow-up reporting: Any relevant additional information obtained by the sponsor that pertains to a previously submitted IND safety report must be submitted as a Follow-up IND Safety Report. Such report should be submitted without delay, as soon as the information is available but no later than 15 calendar days after the sponsor receives the information.

Any reports submitted to the FDA will also be filed with Eiger Biopharmaceuticals within the same timelines prescribed above.

8.15.3 Pregnancy monitoring and reporting

All participants of childbearing potential must follow the contraception requirements listed in section 6.1.1.6 from Day 0 to Day 84. A pregnancy test will be administered at screening to confirm that pregnant women are not enrolled in this study. Female participants will be asked to confirm ongoing use of required contraception and to report pregnancy through Day 84. Male participants will be asked to confirm ongoing use of required contraception and to report pregnancy of female partners through Day 84.

If a female participant or the female partner of a male participant becomes pregnant while on this study, the investigator/ designee will request to follow the pregnancy to its

outcome. Pregnant partners of male participants will not be required to provide records for themselves or their fetus/child but may do so under a separate HIPAA medical records request form if they choose. Pregnant female participants will be required to provide this information for themselves and the fetus/child unless they withdraw consent from this study.

Pregnancy is not reported as an adverse event, however, it will be reported to Eiger Biopharmaceuticals and the FDA as per voluntary reporting requirements.

8.16 Assessment of exposure to SARS-CoV-2 through household survey.

Dose of exposure to SARS-CoV-2 will be assessed through assessment of household size, household relationships COVID -19 exposure and social distancing measures employed within and outside the home assessed at baseline and day 14. If unable to conduct household survey at Day 0, the survey may be conducted by phone anytime before Day 14 evaluation. We will utilize validated survey items from the NIH Public Health Emergency and Disaster Research Response (DR2) repository (<https://dr2.nlm.nih.gov/>).

Surveys are adapted from the COVID-19 Household Environment Scale (https://www.phenxtoolkit.org/toolkit_content/PDF/Behar_Zusman_CHES_ENG.pdf) and the WHO Household transmission investigation protocol for 2019-novel coronavirus (COVID-19) infection.

8.17 Contraception Remote Follow-Up

Females who were of childbearing potential at the time of screening and males with female partners who are of childbearing potential will be contacted by phone, text, or other electronic means available to the participant to confirm that study-required contraception has been used per protocol and that neither the participant or female partner has become pregnant between Day 0 and Day 84.

8.18.1 Remote collection of concomitant medication, adverse events and FLU-PRO.

This will be collected directly in REDCap though a link embedded in the eMocha app. Participants will include their eMocha app username and cell phone number on the survey. For participants who are unable to access or use eMocha, surveys will be interviewer administered over the phone by trained research staff.

9. Study Intervention/ Investigational Product

9.1 Investigational Agent

Lambda Injection, 0.18 mg/syringe (0.4 mg/mL) is supplied in BD Hypak syringes for SC administration of 180 µg. Dummy syringes of saline in equivalent volume of 0.45mL will be made and administered for participants receiving placebo.

9.2 Administration

Subcutaneous injection of Lambda/placebo will be administered by licensed study personnel on Day 0.

9.3 Storage of Investigational agent

Investigational product must be stored refrigerated at 2-8°C and protected from long-term (> 24 hours) exposure to light. Maximum room temperature of 15C-30C permitted up to 8 hrs. Do Not Freeze. Used syringes must be discarded in a biohazard container.

9.4 Blinding of study participants

Participants will be blinded to study intervention. To preserve the blind, participants will be asked to turn away during the first injection. Unblinding will not be permitted in this study.

10. Study Location and Infection Control Considerations

Johns Hopkins Hospital Epidemiology and Infection Control (HEIC) has determined that persons who screen negative for COVID symptoms prior to arrival to an ambulatory setting may be treated with standard precautions. These precautions evolve over time; the study team will follow the precaution requirements in place at the time of each study visit. Current precautions and screening questions can be found on the internal Johns Hopkins website https://intranet.insidehopkinsmedicine.org/heic/novel_coronavirus/clinical_resources.html.

Screening visits and subsequent visits for any participant who is not infected with SARS-CoV-2 and is asymptomatic will take place in the Clinical Research Unit (CRU). Nasal swabs for asymptomatic participants will be performed in the drive-through testing tents, since aerosolizing procedures are not permitted in the CRU. While it is permissible for persons to leave their homes for study visits, this protocol is written to reduce the number of touchpoints for both participants and personnel where possible. Study visits listed in the Schedule of Events as “site or remote” may be performed in the CRU or, in a limited fashion, in the home on a case-by-case basis per investigator judgment.

To support possible remote visits, participants will be sent home on day 0 with the following supplies:

- Eight respiratory sampling test kits to satisfy sampling requirements through Day 14.
- Thermometer
- Pulse oximeter (if available due to limited supply)

On day 0, participants will be instructed on self-sampling for SARS-CoV-2 RT-PCR. For participants who engage in home sampling, these specimens will be picked up by a courier that is

equipped and approved to handle this type of biohazard.

Participants who are found to be infected with SARS-CoV-2 at baseline (Group B) or who become infected during the course of the study (Group A) will not return to the study site until Day 28 or until criteria for discontinuation of infected status is met per HEIC standards, whichever occurs later. In the event that an interim in-person visit is required to evaluate an adverse event, these participants may be seen in an ambulatory setting equipped for encounters with SARS-CoV-2 infected persons. In the event that participants become hospitalized, study evaluations that coincide with clinical care will be abstracted from the medical record. Research-specific evaluations will not continue in the inpatient setting.

11. Risks and Benefits

Potential Risks of Treatment

Identified risks associated with treatment with Lambda based on nonclinical and/or clinical data, as well as potential class effects, include hepatobiliary toxicity (transaminase elevations with or without hyperbilirubinemia) and injection site reactions; potential risks include neuropsychiatric disorders (including depression), cardiovascular events, immunogenicity/hypersensitivity reactions, autoimmune disorders, elevated amylase/lipase, dermatitis, hypersensitivity reaction, injection site reaction, and reproductive risk. Complete information on preclinical and clinical safety data is located in the Investigator Brochure.

Potential Benefits of Participation

Potential benefits include prevention of infection with SARS-CoV-2 infection or reduction in severity of COVID-19 symptoms. It is not yet known whether Lambda will have any benefit in this population.

Alternatives to Participation

The alternative to participation in this study is routine care and monitoring following close contact with an individual with COVID-19.

12. Outcome measures

12.1 Group A Prevention cohort primary endpoint:

- No evidence of SARS-CoV-2 infection at or before study day 28

For the purpose of the study endpoint, SARS-CoV-2 infection is defined as any of the following outcomes:

1. SARS-CoV-2 detected in upper respiratory samples at any of day 7, day 14 or day 21; or
2. New finding of serum antibodies (IgA or IgG) against the SARS-CoV-2 spike protein according to validated specifications and performance characteristics at or prior to day 28.

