9. Study Intervention/ Investigational Product	24
9.1 Investigational Agent	24
9.2 Administration	25

9.3 Criteria for removal from dosing of Lambda.....	Error! Bookmark not defined.
9.4 Storage of Investigational agent.....	25
9.5 Blinding of study participants.....	25
10. Study Location and Infection Control Considerations.....	25
11. Risks and Benefits.....	26
12. Outcome measures.....	26
13. Statistical Considerations.....	27
13.1 Sample Size and Power Considerations.....	27
13.2 Statistical Analysis.....	27
14. Safety Oversight.....	28
14.1 Monitoring Plan.....	28
14.2 Study monitoring.....	28
14.3 Withdrawal criteria.....	29
14.4 Study stopping rules.....	29
15. Protection of Human Subjects.....	29
15.1 Ethical Standard.....	29
15.2 Institutional Review Board.....	30
15.3 Informed Consent Process.....	30
15.4 Participant Confidentiality.....	31
16. Data Management and Monitoring.....	31
16.1 Source Documents.....	31
16.2 Data Management Plan.....	32
16.3 Data Capture Methods.....	32
16.4 Study Record Retention.....	32
17. References.....	33

1. Protocol Synopsis

TITLE: Peginterferon lambda-1a for the prevention and early treatment of SARS-CoV-2 infection

DESIGN: A phase 2b prospective, randomized, single-blind, controlled trial of one subcutaneous injection of peginterferon lambda-1a or placebo for non-hospitalized participants at high risk for infection with SARS-CoV-2 due to household exposure to an individual with COVID-19 and one subcutaneous injection of peginterferon lambda-1a or placebo for non-hospitalized participants with asymptomatic SARS-CoV-2 infection detected at study entry. All participants will be followed for an observation period of up to 10 weeks

DURATION: Participants will be on study for a total of 4 weeks (treatment and observation period).

SAMPLE SIZE: Up to 164 participants will be enrolled in the study for a sample of 110 participants at risk for SARS-CoV-2 infection due to household exposure to an individual with COVID-19 (Prevention Cohort). The treatment cohort sample will be determined by the proportion of asymptomatic persons with SARS-CoV-2 detected at study entry constituting an exploratory cohort.

STUDY CENTER: Johns Hopkins Health System.

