8.4. Administration of Flu-PRO Questionnaire

Participants will be assessed to determine the presence or absence of symptoms consistent with COVID-19 using the CDC defined COVID-19 symptom check list daily. In addition, Flu-PRO, a validated, standardized patient-reported outcome (PRO) symptom scale that comprehensively assesses the symptom experience in acute respiratory symptoms across multiple body systems will be used at enrollment and days 1-14 and 28. This will provide an opportunity to assess for potential symptoms related to Lambda as well as COVID-19.

For remote visits, FLU-PRO will be collected directly in REDCap through a link embedded in the

eMocha app. Participants will include their eMocha app username and cell phone number on the survey. For participants who are unable to access or use eMocha, surveys will be interviewer administered over the phone by trained research staff.

A validated, standardized patient-reported outcome (PRO) symptom scale that comprehensively assesses the symptom experience in influenza across multiple body systems was reported in 2016 by Powers and colleagues at the National Institute of Allergy and Infectious Diseases [18]. The purpose of the InFLUenza Patient-Reported Outcome (FLU-PRO[©]) measure is to comprehensively assess the presence and severity of influenza symptoms across body systems often affected by these viruses. The instrument was created in accordance with drug development recommendations of the US Food and Drug Administration (FDA) [19]. This new instrument yields a profile of scores across six body systems with a total score reflecting overall symptom severity. The questionnaire instructs respondents to rate the severity of 37 influenza symptoms over the past 24 hours, including those related to the nose, throat, eye, chest, head, stomach, fatigue, and body aches/pains. Six items measured the same symptom using different wording in order to select the best performing item for the final instrument. For 32 of 37 items, respondents rated the severity of each symptom on 5-point Likert-type scales from 0 (“Not at all”), 1 (“A little bit”), 2 (“Somewhat”), 3 (“Quite a bit”), to 4 (“Very much”). For the five remaining items, severity is expressed as frequency of occurrence: vomiting or diarrhea (0 times, 1 time, 2 times, 3 times, or 4 or more times), and sneezing, coughing, and coughed up mucus or phlegm on a scale from 0 (“Never”) to 4 (“Always”), with higher scores indicating more severe symptoms.

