8.9. Randomization

Randomization will take place on day 0 after screening activities have been performed and the Investigator or designee has determined that the participant is eligible. Day 0 laboratory tests including blood SARS-CoV-2 RT-PCR results are not part of the eligibility criteria and participants will be randomized without this information. Randomization will be built into the study REDCap database. It will not be known at entry/screening whether participants are part of Group A or Group B since their COVID-19 infection status will not be known until entry/screening specimens are processed. All participants will be randomized in a 1:1 ratio to receive Lambda/Lambda (Arm 1) or Placebo/Placebo (Arm 2). Participants who are not eligible for enrollment into Step 2 (will be removed from protocol therapy Single dose of Lambda or placebo) respectively.

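### Section 9.4 forbids telling a participant the assigned arm, with no exception for medical need or pregnancy.

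*Combined protocol and SAP*

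**What the plan says.** The trial is single-blind (synopsis and Section 5). Section 9.4, whose heading concerns study participants, says that participants are blinded, asks them to look away during the injection, and closes with "Unblinding will not be permitted in this study". It names no exception and no time at which the arm may be disclosed.

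Section 11 gives hepatobiliary toxicity as an identified risk of Lambda, and hypersensitivity and reproductive risk among the potential ones. Contraception is required through Day 84 (6.1.1.6). The remote contact in 8.17 checks that "neither the participant or female partner has become pregnant between Day 0 and Day 84". If a pregnancy occurs, 8.15.3 asks to follow it to outcome and adds: "Pregnant female participants will be required to provide this information for themselves and the fetus/child unless they withdraw consent from this study".

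By contrast, the data that a participant's knowledge of the arm could influence stop at Day 28. Under 8.15, adverse events "will be collected from the time of informed consent through protocol Day 28". Under 8.4, FLU-PRO "will be used at enrollment and days 1-14 and 28".

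**The concern.** A blanket ban is more than an omitted detail. It is an instruction, and following it gives a worse result than departing from it. A participant who has a serious suspected reaction, or who becomes pregnant, may want to know whether the active drug was received. So may an obstetrician or emergency physician outside the health system. The protocol obliges a pregnant participant to hand over her own and her child's information unless she withdraws consent, but nothing allows her to be told her own exposure.

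What is at stake is a participant's access to a fact that bears on her or his care, and the position of staff who would have to breach the protocol to supply it.

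**Working it through.** No figure in the plan bears on this, so the check compares sections.

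1. **Who is blinded.** Sections 5 and 9.4 together say single-blind, with participants as the blinded party. No section says that investigators, pharmacists or laboratory staff are masked, although none says outright that they know the arm. Unblinding in 9.4 therefore most naturally means disclosure to the participant. Telling an outside clinician who acts for the participant comes to the same thing.

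2. **Is there an exception elsewhere?** The sections where one would be expected are 8.15.2 (serious adverse events), 8.15.3 (pregnancy), 8.17 (contraception follow-up), 14.1 to 14.4 (oversight, monitoring, withdrawal, stopping) and 15.3 (consent process). None mentions unblinding or disclosure of assignment.

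3. **Is the need foreseeable from the protocol itself?** Yes. Section 11 names the relevant risks. Sections 8.15.3 and 8.17 ask for pregnancies in participants and in partners of male participants. Section 8.7 sends participants with low oxygen saturation or fast breathing to an emergency room without saying which one.

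4. **Would disclosure tell the participant anything?** Allocation is 1:1 among 164 planned participants, so 164 / 2 = 82 are expected on saline. Assuming that pregnancy is unrelated to arm, a pregnant participant has about an even chance of never having received Lambda, and disclosure would settle that.

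5. **Do other routes close the gap?** In part. Section 16.1 requires the medical record to show the treatments given, so a clinician with access to that chart may see the arm. That does not answer the participant, or a clinician without the chart. Section 15.4 requires the sponsor's written approval before study information goes to an unauthorized third party, and its list of those who may see records does not name treating clinicians.

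6. **What does the blind protect, and until when?** Adverse events (8.15), concomitant medications (8.5), FLU-PRO (8.4), serology (8.12) and the Group A primary endpoint (12.1) run to Day 28. The Group B primary endpoint closes at Day 14 (12.2). The Day 84 contact covers only contraception and pregnancy (8.17). Two features prevent Day 28 from serving as a simple calendar cut-off. Infected participants may return to the site later than Day 28 (Section 10). About two adults per household enrol (13.1), so a participant who has finished may live with one who has not.

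**The case against.** The strongest reply is that little harm remains. The trial is single-blind and gives one injection on Day 0, so no later dosing decision depends on the arm. The documents describe no arm-specific management of a reaction or a pregnancy. Treatments go in the chart, and pregnancies are reported to the manufacturer and the FDA. Pregnancy is excluded at entry and contraception is required, so cases should be few. All of this stands, and it narrows the point to the participant and an outside clinician without chart access. It does not supply a reason for a rule without exceptions. If only participants are blinded, disclosure to participants is exactly what the rule forbids.

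A reader might infer three stronger claims that the documents do not support.

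- *Safety assessment is blocked.* Nothing says that investigators are masked, so causality judgement and FDA reporting are not shown to suffer.
- *The ban runs for a fixed eight weeks beyond the last outcome data.* Counting from Day 28 to the Day 84 contact gives 84 − 28 = 56 days, but Section 9.4 does not define when the study ends. The synopsis says both "Participants will be on study for a total of 4 weeks (treatment and observation period" and "All participants will be followed for an observation period of up to 10 weeks". On the 4-week reading the excess is 28 − 28 = 0 days, and on the 10-week reading it is 70 − 28 = 42. Late Day 28 returns shorten any of these. The calendar gap is therefore not a measure of the problem.
- *The trial has no disclosure route at all.* The consent pages are not in the text reviewed and may promise later disclosure. If they do, 9.4 as worded conflicts with them and still needs correcting.

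**Conclusion.** The point holds as a narrow one about the wording of 9.4. The section should permit disclosure to the participant, or to a treating clinician, for medical need or pregnancy, and should say when routine disclosure becomes possible. This rests on a literal reading of the rule and on unblinding meaning disclosure to participants.

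Its size cannot be put in numbers. The documents give no rate of pregnancy or of serious drug reaction, and the even split between arms only restates the allocation ratio. Sample size, endpoints and analysis are not affected. It is a change worth considering because it is cheap and leaves the default blind in place, not because many participants are likely to be involved.

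**What to change.** Replace the last sentence of 9.4 with:

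*Assignment will not be disclosed to a participant until that participant and any co-enrolled household members have completed Day 28 data collection, except when the investigator judges disclosure to the participant or a treating clinician necessary for medical care or for management of a pregnancy (participant or partner). Date, reason and recipient are logged in REDCap, and the participant is analysed as randomized.*

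Tying the default to completed data collection, rather than to Day 84, matches what the blind protects. It also covers late returns and household members still under observation. Section 16.1 needs no change.

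The cost is two sentences and one log form. Section 8.9 already says "Randomization will be built into the study REDCap database", so the log has a natural home. The downside is that a few participants may learn their arm before Day 28, which could affect their self-reports, home self-sampling or behaviour within the household. The investigator's judgement limits how often this happens, and the log makes it visible at analysis.

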3.2 Primary objective

3.2.1 Prevention cohort.

To estimate the proportion of participants with no evidence of SARS-CoV-2 infection at or before study day 28

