8.11. Upper respiratory specimens for SARS-CoV-2 assessment

All participants in Group A Prevention cohort with onset of symptoms consistent with COVID-19 will be referred for clinical testing of upper respiratory samples for evidence of SARS-CoV-2.

All persons who remain asymptomatic will have study testing with upper respiratory samples for evidence of SARS-CoV-2 at study day 7, 14, and 28. When onsite visit for Day 28 is not on the exact Day 28, the study team will make every effort to have the upper respiratory specimens self-collected Day 28 at the participant's residence.

Specimens obtained will depend on site of collection and availability of swabs. Mid turbinate samples will be collected using a nylon flocked swab using the following steps: 1) inserting the swab into the nose in the horizontal position until gentle resistance is met, 2) leaving the swab in for 10-15 seconds then, rotating the swab, 3) repeating in the other nostril with the same swab. Specimens collected with nasopharyngeal swabs will be done according to standard instructions. The swab will be inserted into the nostril parallel to the palate. The swab should reach a depth equal to the distance from nostrils to outer opening of the ear. The swab will be left in place for several seconds to absorb secretions. The swab will be slowly removed from the nostril while rotating it.

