8.12. Serology for SARS-CoV-2

At entry and day 28, all participants will have blood sampled to detect antibodies against the SARS-CoV-2 spike protein (S1 subunit). Testing will be performed at the Johns Hopkins Pathology Laboratory using the commercial Euroimmun antibody assay according to the manufacturer's recommendation. This assay has been validated by the Johns Hopkins laboratory. 6 mL of blood will be collected for each timepoint.

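### The Group A primary endpoint counts a Day 21 swab that nobody is scheduled to take, leaves out the planned Day 28 swab, and does not say whether clinical PCRs on other days count

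*Combined protocol and SAP*

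**What the plan says.** The primary objective for the prevention cohort (3.2.1) is "To estimate the proportion of participants with no evidence of SARS-CoV-2 infection at or before study day 28". The synopsis and 12.1 then define infection by either of two findings. The first is PCR: "SARS-CoV-2 detected in upper respiratory samples at any of day 7, day 14 or day 21; or". The second is a new IgA or IgG antibody against spike protein, no later than Day 28.

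Sampling is described elsewhere:

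- **8.11, study swabs:** "All persons who remain asymptomatic will have study testing with upper respiratory samples for evidence of SARS-CoV-2 at study day 7, 14, and 28". If the Day 28 visit falls on another day, "the study team will make every effort to have the upper respiratory specimens self-collected Day 28" at home.
- **8.11, symptoms:** Group A participants with "onset of symptoms consistent with COVID-19 will be referred for clinical testing of upper respiratory samples".
- **7.2, schedule:** the columns are Day 7, Days 8-13, Day 14 ± 4, Day 28 ± 4 and Day 84 ± 4. There is no Day 21 column.
- **8.12, serology:** "At entry and day 28, all participants will have blood sampled to detect antibodies".
- **Section 10, hospitalized participants:** "study evaluations that coincide with clinical care will be abstracted from the medical record", and research-only evaluations stop.

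In a paragraph that covers both cohorts, section 13.1 gives Day 14 as the day of the primary endpoint.

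**The concern.** This is the primary endpoint of the cohort that the trial is powered on. Its PCR rule names a day on which nothing is collected and omits a day on which 8.11 makes a special effort to collect. It is also silent on clinical testing. For a participant who falls ill, a clinical PCR may be the only PCR taken, because 8.11 promises study swabs only to those without symptoms.

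Someone will therefore have to decide during or after the trial whether a positive Day 28 swab, or a positive clinical test on Day 10 for example, is an infection. The trial is single-blind and 9.4 describes blinding of participants only, so that decision could be made with the arm known. Expected events are few, so each such decision is visible in the result.

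**Working it through.** **1. Compare the day lists.**

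| Source | PCR days |
|---|---|
| Endpoint (synopsis, 12.1) | 7, 14, 21 |
| Planned study swabs (8.11) | 7, 14, 28 |

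Day 21 is counted but not planned. Day 28 is planned but not counted.

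**2. Could a visit window supply a Day 21 swab?** Day 14 ± 4 gives Days 10 to 18. Day 28 ± 4 gives Days 24 to 32. Day 21 lies in neither. The home kits in section 10 are meant to cover sampling through Day 14, so they do not imply a Day 21 swab either.

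**3. Is the Day 28 swab really planned?** In the text of 7.2 as available, the Day 28 swab cell is empty. The Day 28 Flu-PRO cell is empty too, although 8.4 says the questionnaire "will be used at enrollment and days 1-14 and 28". Merged Day 14 and Day 28 cells are therefore likely. The blank proves nothing, and the point rests on 8.11.

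**4. Apply the rule literally to four participants with negative Day 7 and Day 14 swabs.**

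| Only positive finding | Score under 12.1 |
|---|---|
| New antibody by Day 28 | Infected |
| Day 28 study swab | Not infected |
| Clinical PCR on an unlisted day | Not infected by the day list; no rule stated |
| New antibody in blood drawn Days 29-32 | Inside the 7.2 window, but after the Day 28 limit in 12.1 |

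The second and third rows contradict the headline endpoint. The fourth row shows why serology is only a partial backstop. Section 10 keeps newly infected Group A participants off site until Day 28 or until they meet the criteria for ending infected status, whichever is later, so their blood may be drawn late. The antibody must also be new, so a participant already antibody-positive at entry may have no countable finding.

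**5. The plan's own figures.** Section 13.1 assumes 5% infected on Lambda and 25% or 40% on placebo. A two-sided Fisher exact test at 0.05 reproduces all four stated powers: 80.1% and 99.6% with 55 per arm, 36.1% and 84.0% with 27 per arm. Those figures are not disputed, and nothing here corrects them.

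**6. Per-case sensitivity (illustration only).** Expected counts at 25% v 5% with 55 per arm are 0.25 × 55 = 13.75 (14) and 0.05 × 55 = 2.75 (3). One case moves the risk difference by 1/55 = 1.8 points.

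| Placebo v Lambda, of 55 each | Risk difference | Odds ratio (Lambda v placebo) | Fisher p |
|---|---|---|---|
| 14 v 3 | 11/55 = 20.0 points | (3/52)/(14/41) = 0.169 | 0.007 |
| 13 v 3 (one placebo case missed) | 10/55 = 18.2 points | (3/52)/(13/42) = 0.186 | 0.013 |
| 14 v 2 (one Lambda case missed) | 12/55 = 21.8 points | (2/53)/(14/41) = 0.111 | 0.002 |
| 11 v 3 (three placebo cases missed) | 8/55 = 14.5 points | (3/52)/(11/44) = 0.231 | 0.042 |
| 10 v 3 (four placebo cases missed) | 7/55 = 12.7 points | (3/52)/(10/45) = 0.260 | 0.073 |

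The p-values ignore household clustering, whereas the planned analysis is a mixed logistic model.

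**The case against.** The strongest reply is that the practical effect may be small. An affected participant must be negative on Days 7 and 14 and show no countable new antibody. The per-case shift of 1/55 would apply to any misclassification in a trial of this size. At 25% v 5%, four placebo infections must be lost, with none lost on Lambda, before the unclustered p-value passes the final threshold of 0.0492 in 14.4. At 40% v 5% (22 v 3), losing one placebo case leaves p below 0.0001. All of this stands, and the figures above are only an illustration.

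A second reply is that a fixed list of days may be deliberate. Testing triggered by symptoms could differ by arm if Lambda itself causes fever or myalgia, which 8.15 asks about. That is a fair reason for a sensitivity analysis. It does not rescue the list, because one of its days has no swab and 8.11 does not promise the scheduled swabs to participants with symptoms.

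The documents do not support several stronger readings that a reader might infer:

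- **A loss of power.** Section 13.1 gives 25-40% as the rate expected for the study outcome itself, so no discount for missed infections follows.
- **A bias in a known direction.** A missed placebo case shrinks the effect and a missed Lambda case enlarges it.
- **An endpoint that cannot be scored at all.** The Day 7 and Day 14 swabs and the Day 28 serology can all be applied.
- **A Group A trigger for the interim review.** Section 14.1 counts planned enrolled participants, and enrolment spans both cohorts. Making Group A the trigger would be a design preference.
- **A horizon running to Day 32.** The visit window alone does not move an endpoint stated as at or before Day 28.

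**Conclusion.** The inconsistency is real and must be fixed before the endpoint is scored. The definition names an unscheduled swab, omits a planned one and gives no rule for clinical PCRs. Taken literally, it can classify a PCR-confirmed infection on or before Day 28 as a prevention success.

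The conclusion rests on the day lists in the synopsis, 12.1 and 8.11 and on the windows in 7.2. It does not depend on the blank Day 28 cell. The number of affected participants cannot be derived from the documents. The only size that can be given is per case, 1.8 percentage points on the risk difference, assuming 55 per arm. Day 28 serology reduces the problem by an unknown amount.

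**What to change.** 1. In the synopsis and 12.1, replace Day 21 with Day 28 in the PCR criterion.
2. State in advance that a positive clinical or hospital upper respiratory PCR collected after Day 0 and through Day 28 counts as infection, in line with the headline endpoint.
3. Because symptom-triggered testing may differ by arm, report the number of clinical PCRs by arm. Add a sensitivity analysis limited to the scheduled Day 7, 14 and 28 swabs and Day 28 serology.
4. Make 7.2 and 8.11 agree on the swab days and on whether participants who develop symptoms still have the scheduled study swabs. If they do not, say how they are scored in the sensitivity analysis.
5. State how swabs and blood collected inside the 7.2 window but after Day 28 are scored, identically in both arms, without otherwise changing the Day 28 horizon.
6. In 13.1, give the primary endpoint day by cohort: Day 28 for Group A and Day 14 for Group B.

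The cost is protocol wording and one extra analysis. The Day 28 swab, referral of participants with symptoms and Day 28 serology are already described. Record abstraction is described for hospitalized participants only, so outpatient clinical results may need a stated route into the database. If the Day 28 swab cell in 7.2 is truly empty in the original, it must be marked.
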